## **9.1. Efficacy Assessments**

There will be no efficacy assessments for this study.

## **9.2. Adverse Events**

Planned time points for all safety assessments are listed in the SoA (Section 2).

Additional time points for safety tests (such as vital signs, physical exams and laboratory safety tests) may be added during the course of the study based on newly available data to ensure appropriate safety monitoring.

The definitions of an AE or SAE can be found in [Appendix 4](#).

The investigator and any designees are responsible for detecting, documenting, and reporting events that meet the definition of an AE or SAE and remain responsible for following up AEs that are serious, considered related to the study treatment or the study, or that caused the participant to discontinue the study treatment (see Section 8).

### **9.2.1. Time Period and Frequency for Collecting AE and SAE Information**

- All SAEs will be collected from the signing of the ICF until the follow-up visit at the time points specified in the SoA (Section 2).
- All AEs will be collected from the start of treatment until the follow-up visit at the time points specified in the SoA (Section 2).
- Medical occurrences that begin before the start of study treatment but after obtaining informed consent will be recorded on the Medical History/Current Medical Conditions section of the case report form (CRF) not the AE section.
- All SAEs will be recorded and reported to the sponsor or designee immediately and under no circumstance should this exceed 24 hours, as indicated in [Appendix 4](#). The investigator will submit any updated SAE data to the sponsor within 24 hours of it being available.
- Investigators are not obligated to actively seek AEs or SAEs in former study participants. However, if the investigator learns of any SAE, including a death, at any time after a participant has been discharged from the study, and he/she considers the event to be reasonably related to the study treatment or study participation, the investigator must promptly notify the sponsor.

- The method of recording, evaluating, and assessing causality of AEs and SAEs and the procedures for completing and transmitting SAE reports are provided in [Appendix 4](#).

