**Period 1:**

- Participants will be admitted to the clinical research unit on Day -1 and will remain in-house until collection of the final PK sample on Day 6.
- On Day 1, participants will receive a single dose of 100 mcg nemiralisib.

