**Period 2:**

- There will be a washout of at least 14 days between the administration of nemiralisib in Period 1 and the administration of nemiralisib in Period 2.
- Participants will be admitted to the clinical research unit on Day -1 and will remain in-house until collection of the final PK sample on Day 11.
- From Day 1 to 10 inclusive, participants will receive a single dose of 200 mg itraconazole in the morning.
- On Day 5, participants will receive a single dose of 100 mcg nemiralisib one hour after the dose of 200 mg itraconazole.

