11.2.2. Treatment Emergent Flag for Adverse Events

Flag	Definition
Treatment Emergent	
 • If AE onset date is on or after study treatment start date (for that period) & on or before nemiralisib treatment stop date (for that period) plus 10 days (5 times half life of nemiralisib). • Study Treatment Start Date (for that period) \leq AE Start Date \leq Nemiralisib Treatment Stop Date (for that period) + 10 days . • Where 'study treatment' start date (for that period) refers to the date of the first dose given in that period (i.e. nemiralisib for period 1 and itraconazole for period 2)

NOTES:

- If the study treatment stop date is missing, then the AE will be considered to be On-Treatment.
- Time of study treatment dosing and start/stop time of AEs should be considered, if collected.

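### Minor: AE review is not scheduled at Period 2 admission (Day -1), so adverse events between the periods are first asked about on the day itraconazole starts

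*Protocol*

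**What the plan says.** - **Collection rule.** Protocol 9.2.1: "All AEs will be collected from the start of treatment until the follow-up visit at the time points specified in the SoA" (the schedule in Section 2).
- **Period 1.** In Table 2, AE review is blank on Day -1 and starts on Day 1. Participants "will remain in-house until collection of the final PK sample on Day 6".
- **Period 2.** In Table 3, repeated in SAP Appendix 1, AE review is again blank on Day -1 and starts on Day 1. SAE review, concomitant medication review, brief physical examination and laboratory tests are all marked on Day -1.
- **Between periods.** The schedule shows no visit or contact from Period 1 discharge to Period 2 admission.
- **Timing.** Protocol Synopsis and Section 5.1: "There will be a washout of at least 14 days between the administration of nemiralisib in Period 1" and the second dose in Period 2. No maximum is given. "From Day 1 to 10 inclusive, participants will receive a single dose of 200 mg itraconazole in the morning", and "On Day 5, participants will receive a single dose of 100 mcg nemiralisib one hour after the dose of 200 mg itraconazole".
- **Follow-up.** Table 1 places a visit with AE review 5-10 days after the last itraconazole dose.
- **Treatment-emergent flag.** SAP 11.2.2 counts an AE in a period if its onset is on or after the first dose of that period (itraconazole in Period 2) and "on or before nemiralisib treatment stop date (for that period) plus 10 days". Dosing and AE times are to be considered if collected.
- **Reporting.** Protocol 10.3.2 has AEs listed and summarised by treatment; SAP Tables 3.1 and 3.2 are those summaries.

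**The concern.** A blank AE cell on Day -1 is right in Period 1, because no treatment has been given. In Period 2 the same blank falls on a day that is already inside the collection period of 9.2.1, at least nine days after a nemiralisib dose. The site sees the participant that day and asks about serious events and medication, but the schedule does not ask about ordinary AEs until the next day, when itraconazole starts. It also does not say whether that Day 1 review comes before the dose.

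At stake is the recall and dating of mild events that began after discharge. The first scheduled question about them falls on a boundary that decides which treatment an event is counted under. Safety of nemiralisib alone and with itraconazole is a secondary objective, and the by-treatment AE tables are how it is reported.

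**Working it through.** **Inputs.** Minimum 14 days between nemiralisib doses, and Period 2 nemiralisib on Day 5 (Protocol Synopsis and 5.1); Period 1 discharge on Day 6; last itraconazole dose on Day 10, as Section 5.1 states; follow-up 5-10 days later (Table 1); flag window of nemiralisib date plus 10 days (SAP 11.2.2). The right-hand ends of the AE review arrows cannot be read in the text available, so they are assumed to run to discharge (Day 6 and Day 11).

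**The plan's own figure.** SAP 11.2.2 describes 10 days as five half-lives. Protocol 5.5 gives a half-life of about 40 h: 5 × 40 / 24 = 8.3 days. Ten days is reproduced with 48 h: 5 × 48 / 24 = 10. The 10-day rule is used below because it is the one the SAP applies. The documents state no coverage percentage; the shares below are derived.

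**Timeline, with Period 1 Day 1 as day 1.**
- Period 2 Day 5 = 1 + 14 = day 15.
- Period 2 Day 1 = 15 − 4 = day 11.
- Period 2 Day -1 = day 10.

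**Period 1 gap.** Scheduled review ends on day 6 and resumes on day 11, so days 7-10 (4 days) are unasked until day 11.
- SAP window, days 1 to 1 + 10 = 11: 4/11 = 36%.
- Days before itraconazole, days 1-10: 4/10 = 40%.
- With a 15-day interval, Period 2 Day 1 is day 12, so days 7-11 are unasked: 5/11 = 45%. A longer interval does not raise this share, because the window ends on day 11.

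**Period 2 gap, for comparison.** Follow-up falls on Day 10 + 5 = 15 to Day 10 + 10 = 20. After discharge on Day 11, the unasked days are 12-14 (3 days) up to 12-19 (8 days).

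**Flag at the boundary.** An event dated Period 2 Day 1 meets the Period 2 flag. At exactly 14 days that date is also Period 1 day 11, so it meets the Period 1 flag too; the only tie-break offered is time of day, if collected. At 15 days or more it meets only the Period 2 flag.

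**Windows compared in the main tables.** Nemiralisib alone: Days 1-11, 11 calendar days. Co-administration: Day 1 to Day 5 + 10 = 15, 15 calendar days, of which Days 1-4 are itraconazole only.

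**Effect of adding a Day -1 review (minimum interval).** The first question moves from day 11 to day 10. Days 7-9 remain unasked until then: 3 days instead of 4.

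**The case against.** The strongest reply is that little is lost. Section 9.2.1 still requires all AEs from the start of treatment, so the Day 1 review can pick up earlier events retrospectively. Day -1 already includes SAE review, medication review (Protocol 7.7 asks the reason for use), examination and laboratory tests, and Day 1 has a pre-dose ECG and vital signs. The flag works on onset date, not report date, and nothing suggests that sites date events to the day of questioning. The tables are descriptive, with no formal hypotheses. All of this stands, and it is why the point is minor.

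Three stronger readings may tempt a reader:
- **That 36-40% of nemiralisib-alone events go uncounted.** The figure is a share of days whose questioning is delayed. Reading it as events assumes a constant rate. For drug-related events that is doubtful, since discharge at 120 h is already three half-lives after a single dose (120/40).
- **That Period 1 lacks a closing check that Period 2 has.** Period 2 admission supplies examination, laboratory tests, ECG and AE review over Day -1 and Day 1, and the Period 2 tail has its own unasked stretch.
- **That itraconazole starts without an AE question.** The schedule does not order the Day 1 review and the dose; this is possible but not shown.

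**Conclusion.** The schedule gap is real and small. At the minimum interval, four days after the nemiralisib-alone dose are first asked about on the day itraconazole starts: 36% of the SAP window, or 40% of the days before itraconazole. The share of the SAP window reaches 45% if the interval is 15 days or more. Collection is delayed, not ended, and no planned analysis is invalidated.

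A reader might infer a demonstrated bias that makes nemiralisib alone look safer. The documents do not support that: the unasked stretches in the two periods are comparable in length, and misdating is a possibility, not something the plan builds in. What holds is that the first scheduled question falls on the date where the flag changes treatment, and that the main AE tables compare windows of unequal length and content. The day counts assume that AE review runs up to discharge in each period and that the last itraconazole dose is on Day 10.

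**What to change.** 1. Mark AE review on Period 2 Day -1 in Protocol Table 3 and SAP Appendix 1. Use an open, non-leading question covering the time since Period 1 discharge, and record onset dates before itraconazole starts. The visit already takes place, and Protocol Section 2 allows time points to be added with documentation and approval, without an amendment. This shortens the gap by one day; its main value is that between-period events are asked about and dated before the treatment changes.
2. Alongside SAP Table 3.1, add a by-treatment AE summary limited to onset within 120 h after nemiralisib: Period 1 Days 1-6 and Period 2 Days 5-10. Participants are in-house in both stretches, the windows are equal, and the four itraconazole-only days drop out. The cost is one extra table. It omits later events, which stay in the main table.

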### **9.2.2. Method of Detecting AEs and SAEs**

Care will be taken not to introduce bias when detecting AE and/or SAE. Open-ended and non-leading verbal questioning of the participant is the preferred method to inquire about AE occurrence.

### **9.2.3. Follow-up of AEs and SAEs**

After the initial AE/SAE report, the investigator is required to proactively follow each participant at subsequent visits/contacts. All SAEs (as defined in Section [9.2](#)), will be followed until the event is resolved, stabilized, otherwise explained, or the participant is lost to follow-up (as defined in Section [8.3](#)). Further information on follow-up procedures is given in [Appendix 4](#).

### **9.2.4. Regulatory Reporting Requirements for SAEs**

- Immediate notification by the investigator to the sponsor of a SAE is essential so that legal obligations and ethical responsibilities towards the safety of participants and the safety of a study treatment under clinical investigation are met.
- The sponsor has a legal responsibility to notify both the local regulatory authority and other regulatory agencies about the safety of a study treatment under clinical investigation. The sponsor will comply with country-specific regulatory requirements relating to safety reporting to the regulatory authority, Institutional Review Boards (IRB)/Independent Ethics Committees (IEC), and investigators.
- Investigator safety reports must be prepared for suspected unexpected serious adverse reactions (SUSAR) according to local regulatory requirements and sponsor policy and forwarded to investigators as necessary.
- An investigator who receives an investigator safety report describing a SAE or other specific safety information eg, summary or listing of SAE) from the sponsor will review and then file it along with the Investigator's Brochure and will notify the IRB/IEC, if appropriate according to local requirements.

### **9.2.5. Pregnancy**

- Details of all pregnancies in female partners of male participants will be collected after the start of study treatment and until follow-up.
- If a pregnancy is reported, the investigator should inform GSK within 24 hours of learning of the pregnancy and should follow the procedures outlined in [Appendix 5](#).
- Abnormal pregnancy outcomes (eg, spontaneous abortion, fetal death, stillbirth, congenital anomalies, ectopic pregnancy) are considered SAE.

### **9.3. Treatment of Overdose**

For this study, any dose of nemralisib greater than 100 mcg within a 24-hour time period will be considered an overdose.

GSK does not recommend specific treatment for an overdose of nemralisib. The Investigator (or physician in charge of the participant at the time) will use clinical judgment to treat any overdose.

For this study, any dose of itraconazole greater than 200 mg within a 22-hour time period will be considered an overdose.

GSK does not recommend specific treatment for an overdose of itraconazole. The Investigator (or physician in charge of the participant at the time) will use clinical judgment and the information available in the FDA label to treat any overdose.

In the event of an overdose, the Investigator (or treating physician) should:

1. Contact the Medical Monitor immediately.
2. Closely monitor the participant for AE/SAE and laboratory abnormalities until study treatment can no longer be detected systemically (at least 14 days).
3. Obtain a plasma sample for PK analysis within 7 days from the date of the last dose of study treatment if requested by the Medical Monitor (determined on a case-by-case basis).
4. Document the quantity of the excess dose as well as the duration of the overdosing in the CRF.

Decisions regarding dose interruptions or modifications will be made by the investigator in consultation with the Medical Monitor based on the clinical evaluation of the participant.

### **9.4. Safety Assessments**

Planned time points for all safety assessments are provided in the SoA.

#### **9.4.1. Physical Examinations**

- A complete physical examination will include, at a minimum, assessments of the Skin, Cardiovascular, Respiratory, Gastrointestinal and Neurological systems. Height and weight will also be measured and recorded at screening.
- A brief physical examination will include, at a minimum, assessments of the skin, lungs, cardiovascular system, and abdomen (liver and spleen).
- Investigators should pay special attention to clinical signs related to previous serious illnesses.

#### **9.4.2. Vital Signs**

- Vital signs will be measured in a supine or semi-supine position after 5 minutes rest and will include temperature, systolic and diastolic blood pressure, and pulse and respiratory rate.
- For time points where vital signs are collected in triplicate, only systolic and diastolic blood pressure, and pulse rate should be repeated. There should be at least a 2 minute interval between readings.
- Baseline will be defined as the mean of the 3 pre-dose measurements taken on Day 1 for each Period.

#### **9.4.3. Electrocardiograms**

- 12-lead ECGs will be measured in a supine or semi-supine position after 5 minutes rest.
- 12-lead ECGs will be obtained at each time point during the study, as outlined in the SoA (see Section 2). This will be performed using an ECG machine that automatically calculates the heart rate and measures PR interval, QRS duration, QT and QTcF intervals. Refer to Section 8.1.2 for QTc withdrawal criteria and additional QTc readings that may be necessary.
- At time points at which triplicate ECG are required, 3 individual ECG tracings should be obtained as closely as possible in succession (no more than 2 minutes apart). The full set of triplicates should be completed in less than 4 minutes.

#### **9.4.4. Spirometry**

- Spirometry assessments will be performed whilst the participant is in a seated position (if the assessment is done on a bed, the participant's legs should be over the edge).
- Spirometry assessments will be repeated until 3 technically acceptable measurements have been made. The highest of the 3 values will be recorded in the CRF.
- Refer to Section 8.1.3. for the FEV1 withdrawal criterion.

#### **9.4.5. Clinical Safety Laboratory Assessments**

- Refer to [Appendix 2](#) for the list of clinical laboratory tests to be performed and to the SoA for the timing and frequency.
- The investigator must review the laboratory report, document this review, and record any clinically relevant changes occurring during the study in the AE section of the CRF. The laboratory reports must be filed with the source documents.
- All laboratory tests with values considered clinically significantly abnormal during participation in the study or at the follow-up visit should be repeated until

the values return to normal or baseline or are no longer considered significantly abnormal by the investigator or medical monitor.

- If such values do not return to normal/baseline within a period of time judged reasonable by the investigator, the etiology should be identified and the sponsor notified.
- All protocol-required laboratory assessments, as defined in [Appendix 2](#), must be conducted in accordance with the laboratory manual and the SoA.

## **9.5. Pharmacokinetics**

A 2 mL blood sample for PK analysis of nemiralisib will be collected at each time-point listed in the SoA. A 2 mL blood sample for PK analysis of itraconazole and hydroxy-itraconazole will be collected at each time-point listed in the SoA.

At timepoints where nemiralisib, itraconazole and hydroxy-itraconazole are measured, a single 3 mL blood sample will be collected.

The actual date and time of each blood sample collection will be recorded. Sample storage and shipping instructions will be included in the Study reference manual (SRM) or equivalent.

Analysis of plasma samples for nemiralisib will be performed within PTS-IVIVT-BIB, GlaxoSmithKline. Concentrations of nemiralisib will be determined in plasma samples using the currently approved bioanalytical methodology. Raw data will be archived at GSK.

Analysis of plasma samples for itraconazole and hydroxy-itraconazole will be performed under the control of PTS-IVIVT-BIB/TPR GlaxoSmithKline. Concentrations of itraconazole and hydroxy-itraconazole will be determined in plasma samples using the currently approved bioanalytical methodology. Raw data will be archived at the bioanalytical site for a specified portion of the retention period.

## **9.6. Pharmacodynamics**

Pharmacodynamic parameters are not evaluated in this study.

## **9.7. Genetics**

Genetics are not evaluated in this study.

## **9.8. Biomarkers**

Biomarkers are not evaluated in this study.

## **9.9. Health Economics OR Medical Resource Utilization and Health Economics**

Health Economics/Medical Resource Utilization and Health Economics parameters are not evaluated in this study.

## 10. STATISTICAL CONSIDERATIONS

The primary objective of the study is to characterize the effect of repeat oral dosing of itraconazole on the pharmacokinetics of a single inhaled dose of nemiralisib in healthy participants. No formal hypotheses will be tested.

### 10.1. Sample Size Determination

The sample size has primarily been based on feasibility; however it has also been chosen such that the estimated level of precision achieved for AUC(0-∞) and Cmax is considered to be acceptable.

Variability estimates have been taken from preliminary PK data (with nominal sampling times) for the 207674 study, since it used the same formulation as in this study. The 500mcg dose is the closest to 100mcg, so this has been chosen; indeed variability has been observed to increase with dose, so this is considered a conservative estimate.

Study 207674 observed total between subject standard deviations (SD) on the loge scale of 0.382 for AUC(0-∞) and 0.411 for Cmax. Based on correlation observed in the 201544 study (rho=0.253 and 0.302 for AUC(0-∞) and Cmax respectively) the within subject SD on the loge scale has been assumed to be 0.330 for AUC(0-∞) and 0.343 for Cmax for this study.

It is consequently estimated that with 16 subjects providing the relevant PK parameter data, the upper bound of the 90% confidence interval (CI) will be within approximately 22% of the point estimate and the lower bound within 18% for AUC(0-∞). For Cmax the upper bound of the 90% CI is estimated to be within approximately 23% of the point estimate and the lower bound within 19%. The following gives the expected CIs under the assumption of various ratios between the two groups:

Ratio (nemiralisib co-administered with itraconazole / nemiralisib administered alone)	CI	
	AUC(0-∞)	Cmax
1	(0.82, 1.22)	(0.81, 1.23)
2	(1.64, 2.44)	(1.63, 2.46)
5	(4.10, 6.09)	(4.07, 6.14)

### 10.1.1. Sample Size Sensitivity

If the within subject standard deviation observed in AUC(0-∞) and Cmax is 10% or 20% higher than estimated, the upper and lower bounds of the 90% CI would be as follows:

	% increase in SD	SD	Percentage Within which the 90% CI lies	
			Upper bound	Lower bound
AUC(0-∞)	10%	0.3634	24%	20%
	20%	0.3965	25%	20%
Cmax	10%	0.3773	27%	21%
	20%	0.4116	28%	22%

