## **5.4. Scientific Rationale for Study Design**

This is a drug-drug interaction study in healthy males and females of non-child bearing potential. Participants will be dosed with nemralisib before and during co-administration of itraconazole and will act as their own control. A sufficient wash-out period is included (at least 14-days between nemralisib dose administrations in Period 1 and in Period 2) to remove any effect or residual systemic exposure from the first dose of nemralisib before starting itraconazole dose administration in Period 2.

An open label design was considered appropriate because the primary objective (pharmacokinetic parameters) does not require blinding and no pharmacodynamic markers were included in the study.

Woman of child bearing potential are excluded from participation in this study because itraconazole has shown reproduction toxicity in animal studies. In addition, there is limited information on the use of itraconazole during pregnancy and during post-marketing experience, cases of congenital abnormalities have been reported.

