7.1.5.1. Statistical Methodology Specification

The following pharmacokinetic statistical analyses for nemoralisib will only be performed if sufficient data is available (i.e. if participants have well defined plasma profiles). If $AUC(0-\infty)$ is not calculable for more than 50% of subjects in the PK population in each period, $AUC(0-t)$ will also be analysed for nemoralisib as described below.

Endpoint / Variables

 • $AUC(0-\infty)$ for nemoralisib • C_{max} for nemoralisib
Model Specification

 • The parameters $AUC(0-\infty)$ and C_{max} will be \log_e transformed and analysed separately using mixed effects models. • Treatment Group will be fitted as a fixed effect and subject as a random effect. • The MIXED procedure in SAS will be used with the following options:- 
 ○ The Kenward and Roger method for approximating the denominator degrees of freedom to correct for bias in the estimated variance-covariance. • Nemoralisib co-administered with itraconazole will be compared to nemoralisib administered alone.
Model Checking & Diagnostics

 • Distributional assumptions underlying the models used for analysis will be examined by obtaining box plots and normal probability plots of the studentised residuals and plots of the residuals versus the fitted values (i.e. checking the normality assumption and constant variance assumption of the model respectively) to gain confidence that the model assumptions are reasonable.
Model Results Presentation

 • For each PK parameter:- 
 • Adjusted geometric means and 90% confidence intervals (CI) for each treatment group and standard error (\log_e scale).

- Point estimates and associated two-sided 90% confidence intervals for the ratio of nemiralisib co-administered with itraconazole to nemiralisib administered alone (obtained by back-transforming estimates and 90% CIs for the treatment differences from the statistical model on the \log_e scale) and standard error (\log_e scale).
- The mean squared error (MSE) will also be presented.

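### Protocol 10.1.1: the precision figures for AUC(0-∞) +20% and Cmax +10% are exchanged; separately, the stated precision appears to use 30 df where the SAP model normally gives 15

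*Protocol*

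**What the plan says.** Protocol 10.1 calls the sample size mainly a feasibility choice, supported by the expected precision for AUC(0-∞) and Cmax. It assumes within-subject SDs on the log scale of 0.330 and 0.343. The precision is worked out for a study "with 16 subjects providing the relevant PK parameter data". What it claims for AUC(0-∞) is that "the upper bound of the 90% confidence interval (CI) will be within approximately 22% of the point estimate and the lower bound within 18"%. The matching Cmax figures are 23% and 19%. A table gives the expected CIs at true ratios of 1, 2 and 5. No degrees of freedom are named.

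Protocol 10.1.1 repeats the exercise for the case "If the within subject standard deviation observed in AUC(0-∞) and Cmax is 10% or 20% higher than estimated". Each row lists the increase, the SD, the upper bound and the lower bound:

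- AUC +10%: "10% 0.3634 24% 20"%
- AUC +20%: "20% 0.3965 25% 20"%
- Cmax +10%: "10% 0.3773 27% 21"%
- Cmax +20%: SD 0.4116, 28% and 22%

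On the analysis, Protocol 5.4 says that participants "will act as their own control". SAP 7.1.5.1 says that "Treatment Group will be fitted as a fixed effect and subject as a random effect", with Kenward-Roger denominator degrees of freedom.

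**The concern.** All four rows share one sample size and one confidence level, so the interval has to widen as the SD rises. In order of SD (0.3634, 0.3773, 0.3965, 0.4116) the printed upper bounds run 24, 27, 25, 28% and the lower bounds 20, 21, 20, 22%. No quantile common to the rows can produce that order. The AUC lower bound also stays at 20% while its SD goes from 0.3634 to 0.3965.

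A second question is whether the precision was worked out on the degrees of freedom that the planned paired analysis will have.

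No hypothesis is tested and no precision threshold is set. The stated precision is therefore the only quantitative support for 16 evaluable participants, and 10.1.1 is the only check on how well it holds up.

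**Working it through.** **Inputs.** n = 16 and a 90% CI (Protocol 10.1; SAP 2.4 says two-sided); total SDs 0.382 and 0.411, correlations 0.253 and 0.302, within-subject SDs 0.330 and 0.343 (Protocol 10.1); inflated SDs (Protocol 10.1.1).

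**Within-subject SDs.** 0.382 × √(1 − 0.253) = 0.3302 and 0.411 × √(1 − 0.302) = 0.3434, in line with the text.

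**Formula.** h = t(0.95, df) × SD × √(2/16); upper % = exp(h) − 1; lower % = 1 − exp(−h); CI = ratio × exp(±h).

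**Reproducing 10.1.** With t(0.95, 30) = 1.6973:

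- AUC: h = 1.6973 × 0.330 × 0.3536 = 0.198, giving 21.9/18.0 (printed 22/18).
- Cmax: h = 1.6973 × 0.343 × 0.3536 = 0.206, giving 22.9/18.6 (printed 23/19).
- All 12 CI limits match to two decimals. At ratio 5 they are (4.102, 6.095) and (4.070, 6.143), printed (4.10, 6.09) and (4.07, 6.14). The unrounded AUC upper limit is 6.09496.

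The normal quantile (21.2/17.5 and 22.1/18.1) and t on 15 df (22.7/18.5 and 23.7/19.2) do not reproduce the CI table.

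**Are the SDs in the right rows?** 0.3634/1.1 and 0.3965/1.2 both give 0.3304; 0.3773/1.1 and 0.4116/1.2 both give 0.3430. Labels and SDs agree, so only the percentages are out of place.

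**Sensitivity rows (upper/lower, %).**

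| Row | SD | Printed | 30 df | 15 df |
|---|---|---|---|---|
| AUC +10% | 0.3634 | 24/20 | 24.4/19.6 | 25.3/20.2 |
| AUC +20% | 0.3965 | 25/20 | 26.9/21.2 | 27.9/21.8 |
| Cmax +10% | 0.3773 | 27/21 | 25.4/20.3 | 26.3/20.9 |
| Cmax +20% | 0.4116 | 28/22 | 28.0/21.9 | 29.1/22.5 |

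With 30 df the first and last rows match as printed, and the middle two match once their pairs are exchanged. On that basis an upper bound that rounds to 25% needs an SD between 0.3652 and 0.3785, and one that rounds to 27% needs 0.3917 to 0.4049. With 15 df the ranges are 0.3536 to 0.3665 and 0.3793 to 0.3920, so neither middle row fits that basis as printed.

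**Degrees of freedom under the SAP model.** With 16 complete pairs the treatment contrast has 16 − 1 = 15 df, t(0.95, 15) = 1.7531, unless the subject variance is estimated at zero, when it has about 30. The chance of that is P(F(15,15) < (1 − ρ)/(1 + ρ)): 16% at ρ = 0.253 and 12% at ρ = 0.302. Moving from 30 to 15 df adds 0.8 (upper) and 0.5 (lower) percentage point at base for both parameters. In the sensitivity rows it adds 0.9 to 1.0 and 0.6.

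**The case against.** On the exchange, the best defence is that it is an erratum. All four pairs are valid values, the worst case (28/22) is unchanged, and section 10.1 is not touched. That is fair as to consequence, but it does not make the two rows right. A cell displaced in the copy at hand cannot be wholly excluded, and a glance at the signed protocol would settle it; the SDs and labels, however, sit in their proper rows.

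The df point is open to more argument:

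- **30 df is not uniquely identified.** Sixteen subjects with 31 df, or 17 with 16 df, also reproduce the CI table and the exchanged rows. The 30 df fit is tight at one limit: with SD 0.3304 in place of 0.330, the AUC upper limit at ratio 5 would round to 6.10, not the printed 6.09. This stands, so 30 df remains an inference. The text says 16 subjects, however, and the exchange is the same on all three bases.
- **The SAP analysis may use more than 16 pairs' worth of data.** About 20 are enrolled, and anyone with Period 1 data only still contributes through the random subject effect. With 16 pairs plus 4 such participants, approximate precision is 21.5/17.7 for AUC and 22.6/18.4 for Cmax, no worse than printed. This is a fair limit on calling the figures optimistic. The sentence in 10.1, though, is conditioned on 16 subjects giving the data.
- **The size is under, or about, one point on figures described as approximate.** This also stands, and it is why the df point is secondary.

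**Conclusion.** The concern holds. The exchange in 10.1.1 is certain from the ordering alone, and the corrected pairs (27/21 for AUC +20%, 25/20 for Cmax +10%) do not depend on which of the three bases was used. As printed, a 20% higher SD appears to move the AUC upper bound by 3 points (22% to 25%). The true movement is about 5 points (21.9% to 26.9% with 30 df, 22.7% to 27.9% with 15 df), so the difference comes almost entirely from the misplaced rows.

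The df point also holds as a lesser matter, on two assumptions: exactly 16 complete pairs, and a subject variance estimated above zero. The stated precision is then optimistic by 0.5 to 1.0 percentage point per bound. The exception is the misplaced Cmax +10% row, which is pessimistic (27/21 printed, 26.3/20.9 with 15 df). Neither point alters the case for 16 evaluable participants in any material way.

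**What to change.** 1. In Protocol 10.1.1, exchange the two percentage pairs. On the current basis AUC +20% reads 27/21 and Cmax +10% reads 25/20.
2. State the degrees of freedom behind 10.1 and 10.1.1.
3. To agree with the SAP model, recompute both sections with t(0.95, 15). These values then replace those in item 1. From the printed SDs:
   - Base: AUC 22.7/18.5, Cmax 23.7/19.2.
   - Sensitivity: the 15 df column of the table above.
   - Expected CIs at ratios 1, 2, 5: AUC (0.82, 1.23), (1.63, 2.45), (4.08, 6.13); Cmax (0.81, 1.24), (1.62, 2.47), (4.04, 6.18).

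Give the percentages to one decimal and name the SD used. The base AUC lower bound is 18.497% from 0.330, so whole-number rounding turns on the fourth decimal of the SD. Some CI limits are equally sensitive: SD 0.3304 would give 0.81 at ratio 1 and 6.14 at ratio 5 for AUC.

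The cost is a text correction. Sample size, conduct and analysis stay as they are. The stated precision becomes slightly less favourable, except in the Cmax +10% row, which improves slightly.
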